9.2 Remote monitoring

Remote (source data verification) and/or centralized (data review) monitoring is carried out by sponsor personnel or representatives (e.g., data management personnel, statisticians, or clinical monitors) at a location other than the site(s) at which the clinical investigation is being conducted (evaluation without visiting the

investigation site). Remote monitoring processes can provide many of the capabilities of on-site monitoring as well as additional capabilities.

In addition to onsite monitoring visits, remote monitoring of the data entered in the eCRF system could be used to achieve the following:

- Conduct activities such as: standard checks of range, consistency, and completeness of data and checks for unusual distribution of data, such as too little variance)
- Special attention will be given in case of frequent data anomalies or errors, protocol deviations or excessive dropouts.
- Augment on-site monitoring by performing monitoring activities that can only be accomplished using centralized processes (e.g., statistical analyses to identify data trends not easily detected by on-site monitoring)
- Monitor data quality through routine review of submitted data in real-time to identify missing data, inconsistent data, data outliers, and potential protocol deviations that may be indicative of systemic and/or significant errors in data collection and reporting at the site
- Verify source data remotely, provided that both source data and CRFs can be accessed remotely
- Conduct aggregate statistical analyses of study data to identify subject data that are outliers relative to others and to evaluate individual subject data for plausibility and completeness
- Conduct analyses of site characteristics, performance metrics (e.g., high screen failure rates, high frequency of eligibility deviations, and delays in reporting data), and clinical data to identify early on corrective actions needed for characteristics correlated with poor performance or noncompliance

9.3 Source data verification

Source data is all information in original records, certified copies of original records of clinical findings, observations, or other activities in the clinical investigation, necessary for the reconstruction and evaluation of the clinical investigation. This includes source data initially recorded in an electronic format.

All documents and data related to the clinical investigation handled by site personnel, shall be produced and maintained in a way that assures reliability, integrity, control and traceability, and shall be appropriately stored to provide a complete history.

The Principal Investigator shall assure the accuracy, attribution, completeness, legibility and timeliness of the data reported to the sponsor in the eCRFs and in all required reports. All printed copies of electronic source documents shall be certified, as indicated by a dated signature by the investigational site personnel at the time the document is printed. Special requirements should be applied to the capture, review and retention of electronic source data, to ensure reliability, quality, integrity and traceability.

The data reported in the eCRFs shall be derived from source documents and be consistent with these source documents, and any discrepancies shall be explained in writing. The eCRF can serve as the source document and this must be documented on the Source Data Specification Form. The Source Data Specification Form must be completed at the initiation visit detailing the location of the source data for each data point agreed upon by the principal investigator.

10. Statistical considerations

10.1. Statistical design, methods, and analytical procedures

The primary objective will be evaluated by analysing the primary endpoint, supported by the secondary endpoint of flow-stop, and the secondary objective will be evaluated by analysing the secondary endpoints of adverse events and discomfort.

Baseline assessments and endpoints will be reported by descriptive statistics and/or listed.

Summaries will be presented by device i.e., investigational and comparator device and if relevant, by other grouping variables i.e., HCP and self-catheterisation.

Descriptive statistics for continuous variables are presented with N, Mean, SD (standard deviation), Median, Min and Max, where N denotes the number of subjects contributing with non-missing data. For discrete variables, descriptive statistics are presented with N and percentage, where percentage is based on the total number of subjects/observations with non-missing data.

All statistical analysis will be performed with SAS (version 9.4/Enterprise Guide version 7.1).

10.2. Definition of analysis populations

Screening Failures (SF), Intention to Treat (ITT), Full Analysis Set (FAS), Safety and Per Protocol (PP) analysis set will be defined at a formal data review meeting prior to database lock. As a minimum, the data manager, the clinical manager, and the statistician will be involved in the classification of subjects.

Subjects not adhering to inclusion and/or exclusion criteria are considered screening failures (SF) and are not included and hence not randomised.

- The Safety population will constitute all subjects included i.e., subjects who have given informed consent and fulfils the in- and exclusion criteria.
- The ITT population will constitute all randomised subjects.
- The full analysis set is a modified ITT population i.e., a sub-population of the ITT population, and will constitute all randomised subjects, who have been exposed to at least one device, with at least one endpoint recorded (data non-missing).
- The PP is a sub-population of the full analysis set where all subjects have received treatment as per protocol.

Individual endpoints/data points may be excluded from the analysis, even though the corresponding subject belongs to any of the pre-defined populations. Exclusion of subjects or data points must be documented.

All statistical analysis and test of hypothesis will be based on the full analysis set, and in addition, the primary endpoint will also be analysed in the PP population, whereas adverse events and device deficiencies will be assessed in the safety population.

10.3. Analysis of the primary endpoints

Residual volume at first flow-stop, will be analysed in a linear mixed model (LMM) with subject included as a random component. Evidence of superior effect will be concluded, if the 95% confidence interval of the difference between comparator and investigational device, do not include zero.

The model will include following fixed effects.

- Visit (Visit 1 and 2 of catheterisation)
- Device (comparator and investigational device)

The primary endpoint will be evaluated with the null hypothesis being rejected at a 5% significance level (alpha 0.05).

Analysis of sensitivity

- The primary analysis will furthermore be analysed in the PP population, where subjects have received treatment as per protocol.

- Also, a Wilcoxon signed rank test will be applied the primary analysis, under the assumption of data not being normally distributed.

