10.6. Sample size

Input for the sample size calculations i.e., means and standard deviations are based on three exploratory studies CP322, CP323 and CP324. The studies investigated earlier prototypes of the micro-hole catheter with identical or similar endpoints in populations of both IC users and healthy volunteers.

A sample size for the primary endpoint of residual urine at 1st flow stop (RV1) is judged to be accommodated by 60 subjects with a power of ~ 90%, assuming a difference of 15 mL, a sdcomparator of 50 mL and a sdactive of 15 mL (please see Table 10-1).

Table 10-1 Sample size calculation of Residual urine at 1st flow stop in a cross-over design, solving for varying power and number of subjects, assuming no within subject correlation as a worst-case approach, using proc Power in SAS.

μ (sd) comparator	μ (sd) active	Alpha	Power	Sample size
25 (50)	10 (15)	0.05	71.9 %	40
25 (50)	10 (15)	0.05	81.2 %	50
25 (50)	10 (15)	0.05	87.7 %	60
25 (50)	10 (15)	0.05	92.2 %	70

Taken into consideration a discontinuation of 20%, the endpoint of RV1 is sufficiently supported by randomizing at least 72 subjects.

If the number of subjects contributing to the primary analysis is less than 60 subjects, it must be carefully considered to include additional subjects (subjects replaced), to maintain sufficient power in the primary analysis.

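### The primary mixed model gives both devices one variance although the plan assumes SDs of 50 and 15 mL, so the confidence interval is modestly off when one-visit subjects are unbalanced by device

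*Combined protocol and SAP*

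**What the plan says.** Section 10.3: RV1 "will be analysed in a linear mixed model (LMM) with subject included as a random component". The fixed effects are visit and device. No residual covariance structure, device-specific variance, robust standard error or degrees-of-freedom method is given. Superiority is concluded "if the 95% confidence interval of the difference between comparator and investigational device, do not include zero".

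Section 10.6 sizes the trial "assuming a difference of 15 mL, a sdcomparator of 50 mL and a sdactive of 15 mL", and allows for loss: "Taken into consideration a discontinuation of 20" per cent, with 72 subjects randomised.

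Section 10.2: "All statistical analysis and test of hypothesis will be based on the full analysis set". That set takes in randomised subjects "who have been exposed to at least one device, with at least one endpoint recorded (data non-missing"), so a subject with RV1 under one device only enters the primary model.

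The two sensitivity analyses in 10.3 are a per-protocol repeat of the same model and a Wilcoxon signed rank test, which uses complete pairs.

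**The concern.** A random subject effect plus a single residual variance gives RV1 the same total variance under each device. The plan's own SDs imply variances of 2500 and 225 mL², a ratio of about 11.

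For complete pairs this does no harm, because the device contrast rests on within-subject differences, whose variance the model estimates correctly. A one-visit subject is different: the model treats a lone comparator value and a lone test value as equally informative. If mainly comparator values are missing, two things happen. The fitted common variance falls, because fewer high-variance values remain, and the model understates how much information was lost. The interval is then too narrow. If mainly test values are missing, it is too wide. This interval is the sole pass/fail criterion.

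**Working it through.** **Inputs.** From 10.6: SDs of 50 and 15 mL, 72 randomised, 20% discontinuation. From 5.7: two sequences in blocks of 8. Assumed: 36 subjects per sequence; 0.20 × 72 = 14.4, taken as 14 subjects who have a Visit 1 value only; missingness unrelated to outcome; within-subject correlation 0, 0.3 or 0.5; the same SDs when the means are equal.

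**The plan's own figure.** With correlation 0, the SD of the paired difference is √(2500 + 225) = 52.2 mL. A two-sided paired test of 15 mL then has 59.1% power with 60 subjects in total. The tabulated 87.7% reproduces only with 120 subjects, that is, with 60 read as per sequence. That is a separate matter. Here it shows that the table does rest on these SDs and zero correlation.

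**Formula at correlation 0.** Let c comparator values and t test values be missing at Visit 2, with c + t = 14. Visit 2 then has 36 − c comparator and 36 − t test values, and Visit 1 has 36 of each.

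- Visit weights: w1 = 36×36/72 = 18; w2 = (36 − c)(36 − t)/58.
- Fitted common variance: v = [(72 − c)×2500 + (72 − t)×225]/130.
- Model variance of the device difference: v/(w1 + w2).
- True variance: {w1²(2500 + 225)/36 + w2²[2500/(36 − c) + 225/(36 − t)]}/(w1 + w2)².
- Two-sided error: 2Φ(−1.96 × model SE/true SE).

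*Split 7:7.* w2 = 14.5 and v = 1362.5. Model variance = 1362.5/32.5 = 41.92. True variance = (24525 + 19756)/1056.25 = 41.92. The interval is correct.

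*Split 9:5.* w2 = 27×31/58 = 14.43 and v = (63×2500 + 67×225)/130 = 1327.5. Model SE = √(1327.5/32.43) = 6.40. True SE = √[(24525 + 20794)/1051.8] = 6.56. The ratio is 0.975 and the error 5.6%.

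*Split 14:0.* w2 = 22×36/58 = 13.66 and v = (58×2500 + 72×225)/130 = 1240. Model SE = √(1240/31.66) = 6.26. True SE = √[(24525 + 22354)/1002.1] = 6.84. The ratio is 0.915 and the error 7.3%.

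For correlation above 0, the best-fitting common variance and correlation were used, and the model SE was compared with the sandwich SE.

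| Comparator : test values lost | Model SE / true SE (correlation 0; 0.5) | Two-sided error (correlation 0; 0.5) |
|---|---|---|
| 0:0 or 7:7 | 1.000; 1.000 | 5.0%; 5.0% |
| 9:5 | 0.975; 0.974 | 5.6%; 5.6% |
| 10:4 | 0.962; 0.961 | 5.9%; 6.0% |
| 14:0 | 0.915; 0.912 | 7.3%; 7.4% |
| 5:9 | 1.026; 1.027 | 4.4%; 4.4% |
| 0:14 | 1.093; 1.096 | 3.2%; 3.2% |

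**How often.** If drop-out is unrelated to sequence, the number lost from one sequence is hypergeometric: P(k) = C(36,k)·C(36,14−k)/C(72,14). Then P(k ≥ 9) = 0.186, so a split of 9:5 or worse in either direction has probability 0.37, and half of those cases are conservative. P(k ≥ 10) = 0.067 and P(k = 14) ≈ 0.00001. Weighting the error by these probabilities gives 5.0%.

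**Simulation check** (REML, 20,000 normal data sets per scenario, correlation 0 and 0.5). Complete pairs gave 0.050–0.053. With 14 one-visit subjects all on the test device the error was 0.074–0.076; with all on the comparator, 0.032–0.034. With device-specific variances plus a covariance, and 60 pairs with 12 one-visit subjects split 6:6, 12:0 or 0:12, it was 0.048–0.053. The mean SE was then 0.99–1.00 of the true SD.

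**The case against.** The strongest reply is that nothing goes wrong on average. A reader might infer that keeping one-visit subjects in the full analysis set by itself invalidates the interval or inflates the trial's type I error. The documents do not support that. Complete pairs and even splits give a correct interval, and the average over chance splits is about 5.0%. The excess belongs to particular realised splits. The likely ones are small, and 14:0 practically never arises by chance. This stands.

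Fourteen one-visit subjects is also an upper-end assumption. The plan does not say when its 20% discontinuation occurs. Randomisation precedes the 150 ml bladder-volume check (7.2), so some losses may leave no RV1 value. Visit 2 is 1–7 days after Visit 1 (7.3), scale readings back up damaged profiles (5.4), and withdrawn subjects can be replaced (6.3, 10.6). This stands too.

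A reader might also infer that reported device means would carry wrong intervals. The plan commits only to descriptive statistics by device (10.1), with device-specific SDs, so that does not follow.

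The plan is silent on the residual structure and does not exclude unequal variances. That is true, but a common variance is what the stated model means unless something is added. The signed rank test is untouched by the problem, but it does not decide success.

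On the other side, 5.8 leaves subjects and nurses unblinded and 10.2 allows single data points to be excluded, so device-related imbalance is possible. The documents give no reason to expect it.

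**Conclusion.** The point holds in a limited form. The primary model's common variance conflicts with the plan's SDs of 50 and 15 mL, and this matters only when one-visit subjects are unbalanced by device. The effect is then modest and its direction is known: anti-conservative when more comparator values are lost, conservative when more test values are lost. At a plausible 9:5 the error is about 5.6%. The bounds at 14 one-visit subjects are about 3.2% and 7.4%.

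These figures assume normal data, 36 subjects per sequence, correlation 0 to 0.5, missingness unrelated to outcome, and the planning SDs carried over to equal means, although 10.6 ties them to means of 25 and 10 mL. Fewer one-visit subjects would shrink the effect. Severity is low: an improvement available at almost no cost, not a flaw that threatens the conclusion.

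**What to change.** In section 10.3, keep Visit and Device as fixed effects. Replace the random subject component with an unstructured 2×2 covariance for each subject's two values, indexed by device, with Kenward-Roger degrees of freedom. In PROC MIXED this is `MODEL rv1 = visit device / DDFM=KR; REPEATED device / SUBJECT=subject TYPE=UN;`. Base the primary 95% confidence interval on this model.

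The cost is a line or two of text and one more variance parameter, with no extra data. With complete pairs the device contrast is essentially unchanged: at correlation 0 and 72 pairs both models give an SE of √(2725/72) = 6.15 mL. The simulated error rates near 5% used complete pairs minus 2 as degrees of freedom; Kenward-Roger is the standard choice for this model in SAS.

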3.1. Objective (s)

Primary objective: To demonstrate superiority of the new compact catheter in terms of improved bladder emptying, with the catheterization performed by a health care professional.

Secondary objective: Is to assess safety of the new compact catheter in support of the CE marking

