3.2. Hypotheses

[figure not shown]
The aim is to assert the hypothesis of the superiority of a newly developed compact catheter over Infyna Chic, a conventional 2-eyelet catheter with lower residual volume at 1st flow-stop.

4. Investigational device and comparator

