10.4. Analysis of secondary endpoints

- Number of flow-stop episodes will be analysed, in a generalized liner mixed model (GLMM), with subject included as a random component. Evidence of effect will be concluded, if the lower 95% confidence limit of the risk ratio between comparator and investigational device, is more than 1.
- Average residual volume post catheterisation and discomfort will be presented with Descriptive statistics for a continuous variable (N, Mean, SD (standard deviation), Median, Min and Max.)

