10.1. Level of significance and power

A significance level of alpha 0.05 (2-sided) will be applied.

The power for concluding superiority of the investigational device is at least 90% or higher.

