10.2. Pass/fail criteria

To demonstrate superiority of the investigational device, the null hypothesis of the primary endpoint must be rejected, at a 5% significance (alpha 0.05).

11. Data management

Data management and the final statistical analyses of all measurements described in this protocol are carried out by the Clinical Strategies team, Coloplast A/S.

Data will be collected through an electronic data capturing (EDC) system on electronic Case Report Form (eCRF), a secure, internet-based case report form. This system will be used to record all subject information collected in the investigation for secure data tracking and centralised data monitoring ("remote monitoring") done by monitors, as defined in the monitoring section.

The EDC system used is Rave EDC, version 2022.3.0, delivered by Medidata Solutions Inc. The system is designed to be compliant with the FDA requirements of 21 CFR part 11. It is a validated data management system allowing only qualified and trained personnel to enter the system. The system has full audit trail and electronic signature.

The data management system has restricted role-based access control. The principal investigator or delegate an CRA must be trained in the system prior to getting access. The sponsor will be responsible for training the principal investigator or delegate, in completion of the eCRF. The training is web-based and must be completed before access to the investigation is granted. Training will be documented in the data management system. The data manager will also demonstrate the system on a virtual meeting. Only the principal investigator, or delegate, will be authorised to enter data in the eCRF.

The monitor, using his/her personal login information shall verify all critical data points against the source documents and issue electronic queries for the authorised clinical site personnel to respond, as defined in the monitoring section.

A critical quality control will be performed by the sponsor's data management team and queries issued where needed. Such queries must be resolved by the site personnel.

The principal investigator, using his/her personal login information, shall sign each eCRF before the database can be locked. This must be done after approval from the data management team.

Automated, real-time access to the data enable control on study compliance and safety assessments.

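### Does the primary superiority rule need to say on which side of zero the confidence interval must lie?

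*Combined protocol and SAP*

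**What the plan says.** The primary endpoint is RV1, in mL, after catheterisation by a health care professional. Section 10.3 analyses it in a linear mixed model with visit and device as fixed effects and subject as a random effect. The rule is: "Evidence of superior effect will be concluded, if the 95% confidence interval of the difference between comparator and investigational device, do not include zero". The same section adds: "The primary endpoint will be evaluated with the null hypothesis being rejected at a 5% significance level (alpha 0.05").

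The section headed Level of significance and power sets the sidedness: "A significance level of alpha 0.05 (2-sided) will be applied". The section headed Pass/fail criteria reads: "To demonstrate superiority of the investigational device, the null hypothesis of the primary endpoint must be rejected, at a 5% significance (alpha 0.05").

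For the number of flow-stops, section 10.4 concludes an effect "if the lower 95% confidence limit of the risk ratio between comparator and investigational device, is more than 1", which does state a direction.

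The aim is stated in section 3.1, "To demonstrate superiority of the new compact catheter in terms of improved bladder emptying", and in section 3.2, where the superiority hypothesis is tied to a new catheter "with lower residual volume at 1st flow-stop". Section 10.6 sizes the trial "assuming a difference of 15 mL, a sdcomparator of 50 mL and a sdactive of 15 mL", with planning means of 25 mL for the comparator and 10 mL for the new device.

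**The concern.** A two-sided 95% interval can exclude zero on either side. The sentence in section 10.3 has sufficient form (superiority is concluded if the condition holds), and the condition has no sign. It refers to a difference between the two devices without saying which is subtracted from which. Taken alone, it would call the new catheter superior when the whole interval shows that it leaves more urine behind.

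The contrast with section 10.4 makes the omission more visible, because the supportive endpoint has a complete directional rule and the endpoint that decides the trial does not. At stake would be the meaning of the trial's single success criterion: a literal reader could count a significant result in the wrong direction as a pass.

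**Working it through.** **1. The texts side by side.**

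| Place | What it fixes |
|---|---|
| Section 3.1 | Direction: better emptying with the new catheter |
| Section 3.2 | Direction on the endpoint itself: lower RV1 with the new catheter |
| Section 10.3 | Interval excludes zero, called a superior effect; no sign |
| Level of significance and power | Two-sided 0.05 |
| Pass/fail criteria | Rejection is required to show superiority of the investigational device; no sign |
| Section 10.4 | Flow-stops: lower limit of the ratio above 1 |
| Section 10.6 | Planned means 25 and 10 mL, so comparator minus new device = +15 mL |

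Only section 10.3 is phrased as a sufficient condition. The pass/fail sentence says what must happen for superiority to be shown; it does not say that any rejection is enough. Both sentences use the word superior (or superiority), and sections 3.1 and 3.2 say what that word means here.

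**2. The plan's power figure.** Inputs from section 10.6: SDs 50 and 15 mL, difference 15 mL, within-subject correlation 0, two-sided alpha 0.05, 60 subjects, stated power 87.7%.

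- SD of the difference = √(50² + 15²) = √2725 = 52.2 mL.
- 60 pairs: noncentrality = 15 / (52.2/√60) = 2.23, power 59.1%. This does not match the table.
- 120 pairs: noncentrality = 15 / (52.2/√120) = 3.15, power 87.7%. This matches.
- 60 pairs with the root-mean-square SD, 52.2/√2 = 36.9 mL, used as the SD of the difference: 87.2%, close to the table.

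The mismatch at 60 pairs is a separate question, and the present point does not depend on it. Both bases are carried below.

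**3. How large a wrong-direction result the literal wording would accept.** Half-width = t(0.975, n−1) × SD of difference / √n.

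- n = 60, SD 52.2: 2.001 × 52.2/√60 = 13.5 mL.
- n = 72, SD 52.2: 1.994 × 52.2/√72 = 12.3 mL.
- n = 60, SD 36.9: 2.001 × 36.9/√60 = 9.5 mL.

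A mean RV1 higher with the new device by more than these amounts would give an interval wholly on the unfavourable side.

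**4. No true difference.** Each tail is 2.5%. Literal rule: 2.5% + 2.5% = 5.0%. Directional reading: 2.5%. The gap is the unfavourable tail of the two-sided test that the plan declares.

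**5. Planned difference of +15 mL.** Probability of rejecting on the wrong side:

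- 60 pairs, SD 52.2: 0.0000166 (literal 0.59077, directional 0.59076).
- 72 pairs, SD 52.2: 0.0000063.
- 120 pairs, SD 52.2: 0.00000019.
- 60 pairs, SD 36.9: 0.00000021.

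Stating the sign therefore leaves power for the intended claim unchanged to four decimals.

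**6. New device truly worse (assumed values, 60 pairs, SD 52.2).** If its RV1 were higher by 5, 10 or 15 mL, the literal condition would be met with probability 11.3%, 30.9% and 59.1%. The directional condition would be met in under 0.4% of trials each time. These are probabilities of a significant two-sided test. They become false superiority claims only if the reader also disregards sections 3.1 and 3.2.

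**The case for a change.** The best case for a change is that section 10.3 exists to define when superiority is concluded, and a definition that relies on the reader already knowing what superior means is incomplete. Section 10.4 shows that the authors write the sign when they write a full rule. The order of subtraction is also unstated, so the favourable sign cannot be read from section 10.3 alone. A figure at the head of section 3.2 is not visible and may hold formal hypotheses, but even those would not alter the sentence in section 10.3. The remedy would be short and would cost no power.

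Part of this stands. The sentence in section 10.3 is incomplete taken alone, and naming the lower limit of comparator minus investigational device would bring it into line with section 10.4. Two things do not stand. The pass/fail sentence states a requirement for superiority and does not let a worse device pass. And the probabilities in steps 4 and 6 are not practical error rates, because they arise only for someone who reads one sentence and sets aside the hypothesis it serves. Under section 5.8 the statistician is blinded until database lock, and section 3.2 fixes the direction well before then, so the direction cannot be chosen after seeing the result. Section 21 also commits the sponsor to publishing negative results.

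**Conclusion.** No change to the plan is needed. The wording gap in section 10.3 is real, but sections 3.1, 3.2 and 10.6 fill it in one direction only: lower RV1 with the investigational device. Read with them, the rule is the usual one, a two-sided 95% interval lying wholly on the favourable side, with a 2.5% chance of a false superiority claim when there is no true difference. Making the sign explicit would change no sample size, model, interval or conclusion, and would move the probability of success at the planned difference by less than 0.00002 on every basis tried.

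This rests on the analyst applying section 10.3 together with the hypothesis in section 3.2, which the plan's own use of superiority requires. The tail figures use the SDs in section 10.6 with zero correlation, or the smaller SD of 36.9 mL that comes close to the sample size table; the conclusion is the same under both.
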